12.2.4 Sample Size Estimation

12.2.4.1 Primary Safety Endpoint

The primary safety endpoint is combined safety (VARC-2 defined as a composite of death, stroke, life-threatening or disabling bleeding, acute kidney injury [Stage 2 or 3], coronary artery obstruction requiring intervention, major vascular complication, and valve-related dysfunction requiring repeat procedure), evaluated at 30 days.

Based on published literature of patients undergoing unprotected TAVI (§12.2.2), establishing the expected Control event rate of 25%, and a 37.5% relative margin (absolute delta 9.4%), a Performance Goal (PG) has been set at 34.4% (25% + 9.4%). The primary safety analysis will assess if the Intervention group's safety event rate is significantly less than the PG of 34.4%.

A sample size of 179 evaluable subjects in the intervention group will provide 85% power to determine whether the intervention group meets the PG at the one-sided $\alpha=0.05$ level when using a one-sample z-test of proportions. After accounting for a potential 5% loss to clinical follow-up or dropout from the primary analysis population (As Treated) at 30 days, the total required sample size is 190 subjects in each intervention group. Therefore, the initial randomized sample size of 190 subjects in each intervention group in each phase will have sufficient power to determine whether the intervention meets the safety PG. For Phase II 150 subjects randomized to the TriGUARD 3 and 40- 50 roll-ins will constitute the primary safety population.

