Note: Enrollment in Phase I has been halted after enrolling a total of 258 subjects (54 roll-ins and 204 randomized subjects including 63 controls) based on a recommendation of the DSMB following interim data review at the prespecified interim analysis timepoint. A new generation device designed for increased efficacy, ease of use, and improved safety which will be tested in Phase II (below).

Phase II

In Phase II, up to 295 randomized subjects and 40-50 roll-in subjects will be enrolled at up to 25 sites in the United States (inclusive of sites enrolling subjects in Phase I). No single site will be permitted to enroll more than 20% of all randomized subjects in Phase II.

Subjects with indications for TAVI and who meet study eligibility criteria will be randomized 2:1 (stratified by study site) to one of two treatment arms:

- **Intervention** – TAVI with the TriGUARD 3 CEPD
- **Control** – standard unprotected TAVI.

Randomization will be stratified by implanted valve type (Medtronic vs. Edwards).

No single valve type will be implanted in more than approximately 70% of randomized patients (phase II).

Roll-in subjects (a minimum of 2 and a maximum of 3 Roll-ins per-site) will not be randomized, but will undergo TAVI with the TriGUARD 3 device. These cases will be proctored by a Sponsor representative.

All subjects will be followed clinically in-hospital and at 30 days, undergo diffusion-weighted MR imaging 2 to 5 days post-procedure, and undergo neurologic (NIHSS) testing pre-procedure, post-procedure (2-5 days post-procedure), and at 30 days. A follow-up phone-call to assess the occurrence of death or stroke will be done at 90 days.

The initial randomized cohort will consist of up to 225 subjects. After at least 50% of the initial randomized cohort (approximately 112 subjects) have reached the 30 day primary efficacy endpoint evaluation time point, a sample size re-estimation will be performed in case the conditional power of the trial (assessed by the independent biostatistician) is >40% but <80%, subject to approval by the Sponsor. If this analysis determines that more than 225 randomized subjects will be required to ensure adequate study power, enrollment may continue until the required number of subjects have been enrolled, or until the total subject limit for the study has been reached (whichever occurs first).

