12.2 Sample Size Calculation

12.2.1 Hypotheses

12.2.1.1.1 Primary Safety Hypothesis (Phase I and Phase II reported individually)

The primary safety hypothesis is that the rate of the primary safety endpoint (a composite of death, stroke, life-threatening or disabling bleeding, AKI [Stage 2 OR 3], coronary artery obstruction requiring intervention, major vascular complication, and valve-related dysfunction requiring repeat procedure) in the group undergoing TAVI with either protection device system (Intervention Groups) at 30 days will be less in each device group (TriGuard HDH and TriGUARD 3) compared separately to a performance goal (PG) of 34.4%.

Specifically, the primary safety analysis will assess if the Intervention group's safety event rate is significantly less than the PG of 34.4% using a one-sample z-test of proportions. The formal null and alternative hypotheses to be tested are:

$$H_0: \pi \geq 0.344$$

$$H_1: \pi < 0.344$$

where π is the true safety event rate for the Intervention arm.

The primary hypothesis test will be carried out by comparing the upper bound of the one-sided 95% confidence interval of the primary safety endpoint event rate in the intervention arm to the PG. With the planned evaluable sample size of 179 subjects and a one-sided alpha of 0.05, the critical value for rejection of the null hypothesis is 28.5%: if the primary

safety endpoint occurs in 28.5% or less of intervention group subjects, the performance goal will be met.

After accounting for a potential 5% loss to clinical follow-up at 30 days (including subjects who do not meet As Treated population criteria), the total required intervention group sample size is 190 subjects in each Phase. For Phase II 150 subjects randomized to the TriGUARD 3 and the 40-50 roll-ins will constitute the primary safety population.

Trial success depends on both primary endpoints being met in their primary analysis populations; i.e., the primary safety endpoint must be met in the primary (AT) population and the primary efficacy endpoint must be met in the primary (eITT) population in order for the trial to be declared a success. Because both primary endpoints (safety and efficacy) must be met (i.e., both H_0 must be rejected) for the trial to be declared a success, no adjustment to alpha for multiple endpoints is required for the two primary study endpoints.

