12.4.8 Roll-In Population Analysis

The Phase II Roll-In population will be pooled with the Phase II intervention group for the primary analysis of the primary safety endpoint. The Roll-In patient population will also be

used for a separate analysis of all primary and secondary endpoints and other measures. Additional analyses will evaluate primary and secondary endpoints in the pooled population of Roll-In Subjects plus Evaluable Subjects. The results of all analyses will be reported using descriptive statistics.

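### The safety power statement of 190 randomised device subjects in each phase is wrong as written; Phase I closed with 141, giving about 76–78% power rather than 85% unless its roll-ins are counted

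*Combined protocol and SAP*

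**What the plan says.** Section 12.2.4.1 sets the calculation: expected rate 25%, performance goal 34.4%, one-sided alpha 0.05, one-sample z-test. It states: "A sample size of 179 evaluable subjects in the intervention group will provide 85% power". Allowing 5% loss, it asks for 190 per intervention group and concludes that "the initial randomized sample size of 190 subjects in each intervention group in each phase will have sufficient power". Its next sentence builds the Phase II safety population from 150 randomised TriGUARD 3 subjects and 40–50 roll-ins.

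The synopsis and Section 12.2.1.1.1 test each device separately against the goal and ask for 190 in each phase. Section 5.2 reports that Phase I was halted after "258 subjects (54 roll-ins and 204 randomized subjects including 63 controls").

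On roll-ins, Section 12.4.8 says: "The Phase II Roll-In population will be pooled with the Phase II intervention group for the primary analysis of the primary safety endpoint". The synopsis paragraph on roll-in analysis says the same. Section 12.4.2 covers both devices and includes roll-ins in the safety analysis without naming a phase.

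Section 12.2.1.1.1 compares the upper one-sided 95% bound with the goal. For 179 evaluable subjects it then adds that if the "safety endpoint occurs in 28.5% or less of intervention group subjects, the performance goal will be met".

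**The concern.** This version of the protocol was written after Phase I closed, so the Phase I device count was known. Yet the power sentence still carries the count planned for Phase I (190 of 285 in the synopsis) and extends it to both phases.

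Safety remains a formal test for each device, so the stated power is a live claim about Phase I. At 85% power, a device whose true rate is 25% misses the goal 15% of the time. At 76–78% power it misses it 22–24% of the time. Anyone interpreting a failed Phase I safety test should know which applies. The reader cannot tell, because the sections do not settle whether the Phase I denominator is 141 or 195.

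**Working it through.** **Inputs.** From Sections 12.2.4.1 and 12.2.1.1.1: p0 = 0.344, p1 = 0.25, one-sided alpha 0.05 (z = 1.645), 5% loss. From Section 5.2: 204 randomised, 63 controls and 54 roll-ins in Phase I. From Section 12.2.4.1: 150 randomised plus 40–50 roll-ins in Phase II.

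**Formulas** (one-sample z-test, normal approximation):

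- Critical rate = p0 − 1.645·√[p0(1 − p0)/n]
- Power = Φ{[(p0 − p1) − 1.645·√(p0(1 − p0)/n)] / √(p1(1 − p1)/n)}

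**The plan's own figures, n = 179.** √(0.225664/179) = 0.0355, and 1.645 times that is 0.0584. The critical rate is 0.344 − 0.0584 = 28.56%. The largest passing count is 51/179 = 28.49%, which matches the stated 28.5%. √(0.1875/179) = 0.0324, so power = Φ[(0.094 − 0.0584)/0.0324] = Φ(1.10) = 86.4%. A continuity correction gives 84.5%, and a test held at exact size 5% gives 84.0%. The stated 85% is reproduced. For loss, 179/0.95 = 188.4, so 189; the plan uses 190.

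**Actual counts.**

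- Phase I, randomised only: 204 − 63 = 141; 141 × 0.95 = 134.
- Phase I with roll-ins: 141 + 54 = 195; 195 × 0.95 = 185.
- Phase II as planned: 190–200; after 5% loss, about 180–190.

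**Worked case, n = 134.** 1.645·√(0.225664/134) = 0.0675; √(0.1875/134) = 0.0374; power = Φ[(0.094 − 0.0675)/0.0374] = Φ(0.71) = 76.1%.

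| Safety population | n | Power (normal) | Critical rate |
|---|---|---|---|
| Plan's figure | 179 | 86.4% | 28.6% |
| Phase I, randomised, after 5% loss | 134 | 76.1% | 27.6% |
| Phase I, randomised, no loss | 141 | 78.0% | 27.8% |
| Phase I with 54 roll-ins, after 5% loss | 185 | 87.5% | 28.7% |
| Phase I with 54 roll-ins, no loss | 195 | 89.0% | 28.8% |
| Phase II, 190 enrolled, after 5% loss | 180 | 86.6% | 28.6% |
| Phase II, 200 enrolled, after 5% loss | 190 | 88.3% | 28.7% |

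The exact binomial power of the z-test is 78.9% at n = 134 (37 events or fewer pass) and 79.7% at n = 141 (39 or fewer).

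**The critical value at larger n.** At the 295 cap with 2:1 allocation, about 197 subjects receive the device. With 50 roll-ins that is 247, or about 234 after 5% loss. The critical rate is then 0.344 − 1.645·√(0.225664/234) = 29.3%.

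**The case against.** The strongest reply has four parts.

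*Phase II is not short.* A reader who sees 150 randomised against 190 required might infer that the Phase II safety test is underpowered. The documents do not support that. The sentence after the quoted one names the roll-ins, and the synopsis and Sections 12.2.1.1.1 and 12.4.8 agree. With them the requirement is met. This part of the reply stands in full.

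*28.5% is not a fixed rule.* A reader might infer that 28.5% applies at any sample size. In Phase I that would let through 38/134 or 40/141, with exact type I error of 8.2% or 7.6% instead of 5.7% or 5.3%. But Section 12.2.1.1.1 ties the figure to 179 evaluable subjects and makes the confidence bound the test, and Section 12.4.2 specifies the z-test and does not mention 28.5%. Both adjust to the actual n, so the inflation would arise only from misuse. In planned Phase II the two agree closely: they pass the same event count at n = 180 and n = 190, and 28.5% is stricter by one event at n = 185. This part stands too, leaving only a point of clarity.

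*Phase I may have 195 subjects.* Section 12.4.2 can be read to include its roll-ins, and then there is no shortfall. This stands as a genuine alternative. Against it, Section 12.4.8 is more specific. Section 12.4.2 also includes roll-ins in the ITT safety analysis, which the synopsis excludes, so its wording may be loose.

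*The shortfall is disclosed and Phase I is closed.* The halt is reported several times, and a synopsis footnote says the safety power calculation was done for TriGUARD 3 independently. True, and no enrolment decision changes. But Section 12.2.4.1 still claims sufficient power in each phase.

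**Conclusion.** The sentence in Section 12.2.4.1 is wrong as written for both phases, because neither randomises 190 subjects to the device. The consequence differs by phase. Phase II power is sound at about 87–88%. Phase I power is about 76–78% (79–80% exact) if only Phase II roll-ins are pooled, which is 7 to 9 points below the stated 85%. It is about 87–89% if the 54 Phase I roll-ins count.

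These figures assume a true rate of 25% and loss between 0% and 5%; the 5% is the plan's allowance, not observed Phase I data. They also take the randomised count as a stand-in for the As Treated population, which may differ slightly. The 85% figure and the 28.5% critical value are both correct at n = 179, and nothing here shows an inflated type I error in the plan.

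**What to change.** 1. In Section 12.2.4.1, replace the sentence about 190 randomised subjects in each phase with the actual counts: Phase I, 141 randomised to the device; Phase II, 150 randomised plus 40–50 roll-ins.
2. Reconcile Section 12.4.2 with Section 12.4.8 and the synopsis on whether the 54 Phase I roll-ins enter the Phase I primary safety analysis. Settle this before that analysis is run, since the choice moves the critical rate from about 27.6–27.8% to 28.7–28.8%.
3. State the Phase I power that matches the choice: about 76–78% without roll-ins or 87–89% with them. Keep about 87–88% for Phase II.
4. As a minor clarification in Section 12.2.1.1.1, say that 28.5% is the critical value at 179 evaluable subjects only, and that the one-sided 95% bound from the z-test at the actual n decides, including if Phase II grows towards the 295 cap.

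The change is wording only, with no effect on enrolment or the test. The cost is a less favourable stated power for Phase I if its roll-ins are left out.

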12.2.4.1.2 Primary Efficacy Endpoint

Sample size for assessing superiority of Intervention over Control with respect to the hierarchical composite primary efficacy endpoint was estimated using the following assumptions:

- All-cause mortality or any stroke at 30 days will occur in ~11% of Control subjects and ~6% of Intervention subjects (5% absolute reduction, ~45% relative reduction)
- Among subjects without all-cause mortality or any stroke to 30 days, NIHSS worsening 2-5 days post-procedure will occur in 9% of Control subjects and 6% of Intervention subjects (3% absolute reduction, 33.3% relative reduction)
- Among subjects without all-cause mortality or any stroke to 30 days and without NIHSS worsening 2-5 days post-procedure, MRI findings will occur in 89% of Control subjects and in 73% of intervention subjects (16% absolute reduction, 17.9% relative reduction).
- Among subjects without all-cause mortality or any stroke to 30 days, without NIHSS worsening 2-5 days post procedure, but with MRI findings, lesion volumes can be divided into 3 out of 4 subsets- 0 mm³, >0-50 mm³, >50-150 mm³ and >150 mm³. For these volume subsets, we expect rates of 11%, 7%, 33% and 48%, respectively, in the control group and 27%, 19%, 7.5%, and 46%, respectively, in the intervention group.
- For sample size calculations a relative reduction of 30% is expected in each lesion volume subset, based on the comparison of total lesion volumes between device and control groups in DEFLECT I, MISTRAL C⁷³ SENTINEL⁹ and CLEAN-TAVI⁷⁴.
- The smallest detectable difference in MRI is a single voxel. In addition, inter-rater mean differences between two independent observers was 15% or ~5 voxels (40.5 mm³) in the KSH Methodology/Reproducibility Study (data on file). Accordingly, a meaningful difference to declare a win/lose between MRI lesion volumes was set at a 15% relative difference or a 50 mm³ absolute difference.

- Loss to post-procedure DW-MRI follow-up is expected to occur in 15% of all subjects (due to contraindications to post-procedure DW-MRI [e.g., pacemaker implantation] or subject non-compliance)
- Loss to follow-up for all other reasons is expected to be 5%.
- Overall α (one-sided)=0.025; (see §12.4.2)

To determine the required sample size, calculations were performed by simulating 5000 samples on SAS software postulating the above parameters; mortality and stroke rates and proportions of patients with NIHSS worsening, any MRI lesions and volumes divided to subsets were simulated by a random binary function.

An evaluable sample size of 225 subjects (2:1 randomization with 150 in the Intervention group and 75 new Control subjects) is sufficient to demonstrate superiority of the Intervention group to the Control group for the primary efficacy endpoint when pair-wise comparisons are made between subjects using the Finkelstein-Schoenfeld method,² and outcomes between treatment groups are compared by the chi-square test.

Therefore, the initial randomized cohort sample size of 225 subjects (150 in the Intervention group and 75 new control subjects) will have >80% power to demonstrate superiority of the Intervention group for the primary efficacy endpoint (one sided $\alpha=0.025$). Notably, in several simulations, considering different distributions for lesion volume and different distributions for death/ stroke, the study power remained greater than 80%.

Adding the 63 control subjects already enrolled in REFLECT Phase I for a total of 138 control subjects would increase the power to at least 92% to demonstrate superiority of the primary efficacy endpoint. 5% loss to follow up is included.

12.3 Analysis Populations

12.3.1 Efficacy Intention to Treat (eITT) Analysis Population

The efficacy Intention to Treat (eITT) analysis population is defined as:

- Subjects who are enrolled in the trial and randomized to a treatment group, regardless of treatment actually received AND
- Who do not have conversion to surgery or prolonged cardiac arrest (>3 minutes) prior to the post-procedure DW-MRI

The eITT population of evaluable (i.e., not Roll-In) subjects will be used for the primary analysis of the primary efficacy endpoint, the primary analysis of the secondary hypothesis-driven endpoints, and the primary analysis of all secondary neurologic efficacy endpoints.

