5.4.1.1.2 Primary Efficacy Endpoint- **Phase II**

The primary efficacy endpoint of the study is the **hierarchical composite efficacy endpoint**, determined by pair-wise comparisons among all subjects according to the following pre-specified hierarchy of adverse outcomes:

- All-cause mortality and/or any stroke (fatal and non-fatal, disabling or non-disabling) [evaluated at 30 days]
 - If both had a death/stroke, a time to event analysis by days will determine a win
 - If both patients had a stroke at the same day the comparison moves to the next tier
- NIHSS worsening (increase from baseline) [evaluated at 2 to 5 days post-procedure]
- Freedom from any cerebral ischemic lesions detected by diffusion-weighted magnetic resonance imaging (DW-MRI) 2 to 5 days post-procedure
- Total volume of cerebral ischemic lesions detected by diffusion-weighted magnetic resonance imaging (DW-MRI) 2 to 5 days post-procedure.

Each subject in the intervention group will be compared with each and every subject from the control group based on the above hierarchy according to the Finkelstein-Schoenfeld method.² For example, if Subject A dies or has stroke and Subject B survives free of stroke to 30 days, Subject B wins (score +1) and Subject A loses (score -1). If both subjects die or both have a stroke on the same day, it is equilibrium (score 0). If both subjects survive free of stroke to 30 days, the comparison moves to the next tier of the hierarchy. A lack of an event is given a +1 score. An event which is less severe than the comparison gets a 0 score (for example death vs. stroke)

After all between-subject comparisons have been performed, scores are summed to obtain a cumulative score for each subject, and outcomes between treatment groups are then compared.

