5.4.2.1.7 Secondary Performance Endpoints

The following performance endpoints will be evaluated post-procedure in the Intervention group (Roll-Ins excluded). TriGuard HDH and TriGUARD 3 reported individually:

- Successful device deployment, defined as ability to access the aortic arch with the TriGuard HDH or TriGUARD 3 delivery catheter and deploy the device from the delivery catheter into the aortic arch
- Successful device positioning, defined as ability to position the TriGuard HDH or TriGUARD 3 device in the aortic arch to cover all major cerebral arteries, with proper positioning maintained (verified by fluoroscopy) until the following time points:
 - Final deployment of the first prosthetic valve
 - Final procedure (after any additional post-dilatation or additional valve implantations have been completed, and the TAVR delivery system has been removed)
- Extent of cerebral artery coverage will be reported as:
 - Complete (coverage of all 3 cerebral artery branches)
 - Partial (coverage of 1-2 cerebral artery branches)
 - None

Note: Maintenance of device positioning to each time point and extent of cerebral artery coverage will be evaluated by the Angiographic Core Laboratory.

- Device interference, defined as interaction of the TriGuard HDH or TriGUARD 3 device with the TAVI system leading to:
 - Inability to advance or manipulate the TAVI delivery system or valve prosthesis, OR
 - Inability to deploy the TAVI valve prosthesis, OR
 - Inability to retrieve the valve prosthesis or delivery system
- Successful device retrieval, defined as ability to retrieve the TriGuard HDH or TriGUARD 3 CEPD.
- Technical success, defined as successful device deployment, device positioning, and successful device retrieval in the absence of device interference
- Procedure success, defined as technical success in the absence of any investigational device-related or investigational procedure-related in-hospital procedural safety events

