9.10 Expected Adverse Events

As with any endovascular intervention, TAVI involves some risks and possible complications. The following anticipated events have been identified as possible complications of TAVI procedures:

- Acute cardiovascular surgery (need for)
- Acute coronary artery occlusion
- Acute myocardial infarction
- Acute neurological events such as stroke, transient ischemic attack (TIA), and encephalopathy
- Allergic reaction to contrast, antiplatelet therapy or device component materials
- Angina pectoris
- Anesthesia reactions
- Aneurysm or pseudoaneurysm
- Arteriovenous fistula
- Ascending or descending aorta trauma
- Atrial or ventricular arrhythmias or fibrillation or sustained heart palpitations requiring therapy
- Bleeding complications such as hematoma and hemorrhage
- Blood loss requiring transfusion
- Bowel ischemia
- Coronary artery or other vascular injury, dissection, or perforation (which may require repair)
- Embolism (air, tissue, device, or thrombus)
- Fever
- Femoral nerve damage
- Hemodynamic changes
- Hypertension or hypotension (sustained requiring therapy)
- Infection, including endocarditis and septicemia
- Pain (at the femoral puncture site, abdominal, back, or other)
- Percutaneous coronary intervention (need for)
- Peripheral ischemia, peripheral nerve damage

- Pulmonary edema
- Pyrogenic reaction
- Renal complications, injury, or failure
- Unstable angina
- Vascular complications which may require vessel repair
- Vessel spasm (sustained, not responding to therapy)

In addition to the risks listed above, the potential risks specifically associated with the TriGuard HDH or TriGUARD 3 procedure include, but may not be limited to, the following:

- Dissection of the innominate artery by improper manipulations, disruption or migration of the TriGuard HDH CEPD filter due to passage of other instrumentation, e.g.: balloon, stent, catheter, wire
- Blue toe syndrome or blue discoloration of a toe
- Femoral bleeding at the access site
- Local trauma to the aortic wall due to device migration

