15% Missing in MRI Follow-up and 5% missing for all other parameters

Type I Error = 5%

The primary analysis population for the primary endpoint is the efficacy Intention to Treat (eITT) population (§12.3.1), which excludes subjects with conversion to surgery or prolonged cardiac arrest prior to the post-procedure DW-MRI. Selection of this population as the primary analysis population for the efficacy endpoint ensures that, should a small number of subjects experience an adverse endpoint event due to circumstances unrelated to procedural neuroprotection, the study will remain powered to detect a clinically-meaningful treatment effect, particularly regarding the volume of subclinical cerebral ischemic lesions on DW-MRI.

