- Operative risk (by Society of Thoracic Surgeons [STS] Risk Score)
- Type and duration of antiplatelet therapy:
 - Pre- and peri-procedural therapy:
 - Protocol-recommended antiplatelet therapy vs. other
 - Maintenance therapy:
 - Dual antiplatelet therapy (DAPT) to 90 days vs.
 - Monotherapy (aspirin or clopidogrel) to 90 days vs.
 - Warfarin with antiplatelet therapy to 90 days vs.
 - Other

As above, analysis of variance on the cube root transformation for total lesion volume data and logistic regression for death/stroke and NIHSS worsening will be used, and a 0.15 level of significance will be used to assess the significance of the interaction.

If the primary efficacy endpoint is met in the primary (eITT) analysis population, sequential testing of the primary efficacy hypothesis will be conducted in the ITT analysis population of evaluable subjects (Roll-In patients are excluded.) As a secondary analysis, the primary efficacy endpoint and its components will be evaluated in the ITT analysis population of evaluable subjects (Roll-In patients are excluded). As an additional analysis, the primary efficacy endpoint will be evaluated in the PT population of subjects with available data.

An additional analysis of the primary efficacy endpoint will also be performed in the primary eITT analysis population with adjustment for pre-existing cerebral lesion volumes. The adjustment will be performed using a quantile regression with the resultant score being the dependent variable and group and the pre-existing cerebral lesion volumes will be independent. Specifically, the PROC QUANTREG procedure will be used to model the median of the score with QUANTILE=0.5 option.

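### The primary efficacy population drops randomised subjects after conversion to surgery or prolonged cardiac arrest, so deaths and strokes in those subjects leave Tier 1 and the efficacy half of the success rule

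*Combined protocol and SAP*

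**What the plan says.** Section 12.3.1 defines eITT as all subjects randomised, whatever treatment they received, "Who do not have conversion to surgery or prolonged cardiac arrest (>3 minutes) prior to the post-procedure DW-MRI". This population "will be used for the primary analysis of the primary efficacy endpoint, the primary analysis of the secondary hypothesis-driven endpoints". Under section 5.4.2.1.1 those secondary endpoints include all stroke, and death or stroke, at 7 days.

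Tier 1 of the hierarchy (section 5.4.1.1.2) is "All-cause mortality and/or any stroke (fatal and non-fatal, disabling or non-disabling) [evaluated at 30 days".

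Section 12.2.3 justifies the population on the ground that, "should a small number of subjects experience an adverse endpoint event due to circumstances unrelated to procedural neuroprotection", power is kept, particularly for lesion volume on DW-MRI.

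The success rule is in section 12.2.1.1.1. Safety must be met in the As Treated population, and "the primary efficacy endpoint must be met in the primary (eITT) population in order for the trial to be declared a success". Section 12.4.3 adds that, once eITT has succeeded, "sequential testing of the primary efficacy hypothesis will be conducted in the ITT analysis population of evaluable subjects". No section says what follows if that ITT test fails.

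**The concern.** Conversion and arrest happen after randomisation and, in the device arm, can follow device exposure. The definition does not ask whether the device contributed, although the Clinical Events Committee already adjudicates relatedness for safety endpoints (section 5.4.2.1.2). A subject who arrests on the table and dies is removed from the comparison instead of being scored as a Tier 1 loss.

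The protocol describes device effects that could plausibly lead to these events. Section 5.4.2.1.7 defines device interference to include "Inability to deploy the TAVI valve prosthesis, OR", and section 9.10 lists "Local trauma to the aortic wall due to device migration" among the device-specific risks. Neither section links the device to conversion or arrest, so these are plausible routes, not documented ones.

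The stated rationale is mainly about MRI volume. That could support treating the MRI tiers as missing for these subjects. It does not support removing deaths and strokes, which are decided before the hierarchy reaches MRI.

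If the device arm has more of these events, the primary test and the gated stroke and death/stroke tests will not register the harm, and the comparison tilts towards the device.

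**Working it through.** **Inputs from section 12.2.4.1.2.** 150 versus 75 subjects, or 138 controls with Phase I pooled; one-sided alpha 0.025. Tier 1 is 11% control and 6% device; Tier 2 is 9% and 6%. The lesion-volume classes (0, >0-50, >50-150, >150 mm³) are 11/7/33/48% and 27/19/7.5/46%. There is a 30% relative volume reduction within classes, and a volume win needs a 15% or 50 mm³ difference. DW-MRI is missing in 15%, and other loss is 5%.

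**Assumptions not in the documents.** Event day is uniform over 0-30. Volume is uniform within class, with the top class 150-1000 mm³.

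**Step 1: reproduce the stated power.** The four-tier Finkelstein-Schoenfeld score was simulated with permutation variance, rejecting at z > 1.96. Power is 0.84-0.88 at 150 versus 75 (plan: above 80%) and 0.94-0.96 with 138 controls (plan: at least 92%). Without the 30% reduction it falls to 0.55-0.63 and 0.72-0.78, so that input must be included.

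**Step 2: effect on Tier 1.** Planned device events are 0.06 × 150 = 9. Suppose 9 events remain in eITT, x further device subjects are removed, each with a death or stroke, and the control rate stays at 11%. Then eITT shows 9/(150 − x) and all randomised show (9 + x)/150.

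| x | eITT rate | ITT rate | Relative reduction, eITT | Relative reduction, ITT |
|---|---|---|---|---|
| 3 | 9/147 = 6.1% | 12/150 = 8.0% | 44% | 27% |
| 6 | 9/144 = 6.3% | 15/150 = 10.0% | 43% | 9% |
| 7 | 9/143 = 6.3% | 16/150 = 10.7% | 43% | 3% |

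**Step 3: effect on the primary test.** Assume conversion or arrest in 2% of each arm, plus a device-arm excess, with half of these subjects having death or stroke. eITT drops them and ITT keeps them.

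| Device excess | 150 vs 75: eITT / ITT | 150 vs 138: eITT / ITT |
|---|---|---|
| 0% | 0.86 / 0.83 | 0.95 / 0.94 |
| 2% (3 subjects) | 0.84 / 0.79 | 0.96 / 0.92 |
| 4% (6 subjects) | 0.85 / 0.74 | 0.94 / 0.85 |

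A separate run of 1,500 trials per cell gave 0.86/0.84, 0.85/0.79 and 0.84/0.74 with 75 controls, and 0.94/0.93, 0.95/0.91 and 0.95/0.87 with 138. Differences of a point or two are simulation noise. eITT power hardly moves as the excess grows; ITT power falls.

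The share of one half matters. If there is no background and every excess subject has a death or stroke, eITT stays at 0.88 while ITT falls to 0.77 at 2% and 0.67 at 4%. With 138 controls eITT is 0.96, and ITT is 0.91 and 0.82.

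**Step 4: can the safety endpoint catch it?** The test compares the upper one-sided 95% limit, p + 1.645√(p(1 − p)/n), with 0.344 at n = 179. With 51 events, p = 0.285 and the limit is 0.340, so it passes. With 52, p = 0.291 and the limit is 0.346, so it fails. This agrees with the protocol's 28.5% critical value. At the assumed 25% rate, 0.25 × 179 ≈ 45 events are expected, which leaves room for 51 − 45 = 6 more.

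**The case against.** The criteria are prespecified and identical in both arms. The excluded events are not lost to the trial: they appear in the sequential ITT test, in the ITT secondary analysis and in As Treated safety. The documents give no rate and no evidence of imbalance, and with equal rates eITT and ITT nearly agree. All of this stands, and it makes the bias conditional.

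Some stronger readings are tempting but not supported:

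- A reader might infer that trial success needs only the eITT result. Section 12.2.1.1.1 also requires the As Treated safety endpoint, which counts all-cause death and any stroke with no exclusion for conversion or arrest. That is a partial safeguard. It has no control comparison, and Step 4 shows that it can absorb about six extra events.
- A reader might infer that all device-related deaths and strokes leave Tier 1. Only those in subjects with conversion, or arrest over 3 minutes, before the DW-MRI do so.
- A reader might cite the dissection risk in section 9.10 as a further route. That item concerns the innominate artery and names the HDH filter, whereas Phase II tests TriGUARD 3, which has no innominate stabiliser.
- A reader might note that operators are not on the blinded list in section 6.3. The documents show no way in which these criteria would be manipulated.
- A reader might suppose that ITT costs nothing. It costs a little power when events are balanced, which is the dilution that the sponsor's rationale has in mind.

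**Conclusion.** The point holds in this form: the primary efficacy analysis conditions on post-randomisation events that the device could plausibly influence, and nothing in the efficacy success condition brings the removed deaths and strokes back.

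The bias is possible, not demonstrated. On the half-with-death-or-stroke assumption, a device excess of 2-4% opens a gap between eITT and ITT power of about 5-11 points with 75 controls and 4-9 points with 138. On Tier 1 alone, six or seven removed device-arm events would hide the loss of nearly all the planned benefit. These figures rest on assumed rates, an assumed share with death or stroke, and assumed volume distributions. It should be corrected before unblinding, because it sits in the success rule and is inexpensive to repair.

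**What to change.** 1. Make ITT (all randomised, roll-ins excluded) the primary population for the primary efficacy test, the efficacy condition in section 12.2.1.1.1, and the gated 7-day stroke and death/stroke endpoints. At minimum, require ITT success as well as eITT success.
2. For subjects with conversion or arrest, score Tiers 1 and 2 as observed and treat only the MRI tiers as missing.
3. Keep eITT as a sensitivity analysis and report its exclusions by arm. State when its window closes for subjects who never have a DW-MRI; the current definition does not, although 15% are expected to miss it.

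Cost: changes of wording in the protocol and SAP, since both analyses are already planned. If the events are balanced at the assumed 2%, the power loss in the Step 3 runs is about 1-3 points (0.86 to 0.83 or 0.84 with 75 controls; about one point with 138), which stays above the stated 80%.
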